Study: # 6850 entitled A sequenced behavioral and medication intervention for cocaine dependence

PI: [name]

NCT# NCT01986075

Statistical Analysis Plan created on Date: 7/05/2012

export data files that are easily read by statistical software packages.

**C7. Data Analysis:** [name], a Biostatistics Faculty member assigned to our division, has extensive experience in the analysis of clinical trial data and will design and oversee all analyses. The primary analyses in this study will be on the intent-to-treat (ITT) sample, (i.e. on all 100 randomized patients). Prior to conducting hypotheses testing we will examine all variables for the presence of outliers and deviations from normality, and transformations will be employed, if necessary. The distribution of demographic variables (ethnicity, sex, age) will be examined and described in terms of means, standard deviations, proportions and 95% confidence intervals. [Demographic and baseline clinical variables will also be examined as predictors of the primary outcome measure, and those found to be significant will be considered as covariates.]

C8. Power Analysis: [Enrolling 155 patients will afford adequate power (80%) to detect medium effect sizes (d=0.57; Odds Ratio=2.8) in the logistic regression analyses investigating response to the behavioral intervention at week 4.] Also, prior studies with amphetamine (Grabowski et al., 2001) and TES (Bickel, Marsch et al., 2008) suggest medium effect sizes can be reasonably expected. Continuous abstinence during treatment is a desired clinical outcome as it predicts continued abstinence during post treatment follow-up (Higgins et al, 2000). We found 33.3% of the MAS-ER/topiramate group and 16.7% of the placebo group achieved 3 weeks of continuous abstinence in our controlled pilot study. The response was 37% in the MAS-ER/topiramate group compared to 7.4% in the placebo group among the high users. We expect our placebo response to be low since individuals randomized to a medication arm will have already demonstrated little response to the CRA+CM therapy alone, the only active component in the CRA+CM/PLACEBO condition. Thus, we conservatively estimated the power (80%; significance  $\alpha$ =0.05) with an expected response rate of 37% in the ehancement medication arm (MAS-ER) compared to 10% among those receiving PLACEBO. The primary outcome for the phase 2 analyses is the percentage of subjects who achieve continuous 3-weeks abstinence during the study. With 34 subjects in each treatment there is 80% power to detect a difference in proportions (37% vs.10%). With 50 subjects in each arm there is 90% power to detect the same difference.

**C9.** Intent to Treat/ Dropouts and missing data: The primary analyses will be on the Intent-to-treat (ITT) sample, (i.e., all randomized subjects according to the treatment they were assigned). We will account for dropouts by examining the primary outcome variables using (longitudinal) mixed effects models (MEM) (Brown and Prescott 1999; Diggle et al 2002) using PROC GLIMMIX in SAS®. MEMs do not require a complete set of time points to estimate the outcome variable. However, inferences from analyses with missing data are valid provided that the data are "missing at random" (Little and Rubin 1987). While 'missing at random' (i.e, the missing mechanism does not depend on the value of the unobserved outcome) is un-testable in most medical research, parametric or semi-parametric models (that both depend on the unobserved outcome value) can be used to model the missingness (Diggle and Kenward 1994; Kenward 1998; Liu et al 1999; Rotnitzky et al 1998; Scharfstein et al 1999). Comparisons of the inferences from the various models of missingness provide a measure of the validity of the 'missing at random' assumption. One can also compute a local sensitivity index which measures the change in the estimated treatment effect in a neighborhood of the 'missing at random' model (Rotnitzky et al 2001). We plan to perform a *sensitivity analysis* based on these two approaches to assess the effect of the assumption of missing 'at random' on the inference.

**C10. Primary Outcome Measures:** The primary outcome measure will be a binary indicator (yes or no) of at least 3 weeks of urine toxicology confirmed self-reported abstinence during Phase-2 (weeks 5-14). While the standard method for measuring cocaine use outcomes is urine toxicology, self-reported cocaine use confirmed by urine toxicology provides additional data that cannot be determined by laboratory testing alone. The reliability of self-reported cocaine use in the context of confirmatory urine toxicology testing is high; for example among 121 cocaine-dependent outpatients self-report matched the toxicology results 94% of the time (Carroll, et al., 2004). Self-reported cocaine use data will be collected using the timeline followback method for the 28 days preceding study entry and each day of the study period. Semi-quantitative urine benzoylecgonine (BE) levels will be obtained with Abbot/ADX technology. To prevent overestimation of cocaine use, we will confirm self-reported cocaine use with a modified version of a procedure developed by (Winhusen et al. 2007), a procedure we have employed in previous studies (e.g. [name] et al., in press). Self-report of cocaine use will be accepted as a "use day" and urine samples with BE levels equal to or greater than the standard NIDA 300 ng/ml will be considered positive. A urine sample will be considered negative if it is preceded within two days by a sample with 2x or more its BE level. If none of the three days preceding a positive urine sample has been self-reported as a use day, the day immediately preceding the sample will be labeled a use day.

Primary hypothesis: A greater proportion of patients treated with CRA+CM/MAS-ER will achieve continued abstinence compared to patients treated with CRA+CM/PLACEBO. The effect of treatment on the

Research Strategy Page 101

outcome (at least 3 consecutive weeks of urine toxicology confirmed self-reported abstinence) will be examined using logistic regression adjusted for covariates (e.g., baseline days/week of cocaine use):  $logit(Y_{ikt}) = \beta_0 + \beta_1 I_{ij}^M + \beta_2 Z_{ijk} + e_{ijk}$ ; where  $Y_{it}$  is a binary outcome indicating 3 weeks of abstinence ( $Y_{itk} = 1$ , when a given individual in a treatment condition is abstinent),  $I_{ij}^M$  is an indicator for the medication treatment ( $I_{ij}^M = 1$  for MAS-ER and  $I_{ij}^M = 0$  for PLACEBO), ),  $Z_{ijk}$  is a vector of covariates, such as baseline cocaine use, and demographic characterisitics (age, gender, ethnicity), and  $e_{ijk}$  is random error. [Covariate by treatment interactions will be tested for significance and the main effect, the primary hypothesis will be answered by testing the null hypothesis  $B_1=0$ . ]

- **[C11. Predicting Responder and Non-Responder status.** Analyses will be conducted to identify variables that may help predict who is more or less likely to respond to the psychosocial intervention alone. Identifying key cognitive-verbal mechanisms (see below) that predict treatment response can help provide important avenues for guiding future therapy development. This important aim will be examined using a logistic regression model within a general linear model framework where responder status at the end of week 4 is a binary outome and the predictors will be a vector of baseline covariates. Predictor variables will be entered in blocks and tested for significance (baseline commitment language, executive functioning, implicit cognition, coping skills, baseline cocaine use, and demographic characteristics (age, gender, ethnicity). Furthermore, a vector of variables representing the magnitude of change in the cognitive, behavioral, and verbal mechanisms will be tested. This later block of variables will evaluate if the response to the behavioral intervention alone is predicted by the magnitude of change in the key cognitive, verbal, and behavioral indices.]
- [C12. Secondary hypotheses and outcomes: Patients receiving CRA+CM/MAS-ER will demonstrate a greater reduction in cocaine use, cravings, and withdrawal symptoms, increased retention and quality of life compared to patients treated with CRA+CM/PLACEBO. Analyses will test the hypotheses that the CRA+CM/MAS-ER group will demonstrate 1) a lower proportion of weekly urine toxicology samples testing positive for benzoylecgonine (longitudinal continuous variable); 2) lower cocaine withdrawal symptoms as measured by the Cocaine Selective Severity Assessment (CSSA; a longitudinal continuous variable), 3) lower cocaine craving as measured by the Cocaine Craving Questionnaire (longitudinal continuous variable) 4] better quality of life (Endicott et al., 1993), and 5) greater study retention then the PLACEBO/CRA+CM group. The longitudinal continuous outcomes will be treated with longitudinal mixed effect models (MEM), where patients will be treated as a random factor. Appropriate transformations of distributions will be applied to the outcome variable if needed (for count variables, the Poisson distribution will be used). The group differences in retention is operationalized as time to dropout, which will be analyzed within a Cox proportion hazard framework. **Exploratory Analyses:** We will also test for differences in treatment outcome between the CRA+CM only condition (no medication or placebo) and each of the medication treatment arms (CRA+CM/MAS-ER and CRA+CM/PLACEBO) on the primary and secondary outcomes outlined above. Recall, this group will consist of the individuals who responded to the behavioral treatment during the 4-week run-in and were not randomized to receive either MAS-ER or PLACEBO. These exploratory comparisons will provide useful information on the relative differences between individuals needing an integrative treatment strategy against those benefiting from the behavioral treatment alone in terms of their trajectory and level of change during a treatment episode.
- [C13. Exploratory hypotheses: Investigating Mechanisms of Change: We propose a set of exploratory analyses to evaluate the predictive and/or moderating relationship of several key cognitive, verbal, and behavioral mechanisms on treatment response. These variables will be assessed at Baseline, Week 5 (beginning of the medication phase), and Week 14 (end of study). They include: COGNITIVE MECHANISMS. A. Executive Functioning. Self-regulation has been linked to higher order cognitive processes under the rubric of executive functioning, which predicts treatment response (Aharonovich et al., 2006). Within this domain several constructs have been implicated in substance use and treatment response 1. Working memory (Letter-Number Sequencing, Wechsler, 1997), improved working memory is associated with enhanced striatal dopamine release (Backman et al., 2011) and has been implicated as being an important process in treatment outcome (Bickel et al., 2010); The letter number sequencing task will be utilized to assess a participant's working memory. 2. The discounting of delayed rewards (Delayed Discount Program, Robles et al., 2008): Working towards greater delayed rewards in contrast to smaller more immediate rewards is a hallmark characteristic of planned, controlled behavior. However, drug dependent individuals discount future rewards faster than non-dependent individuals and the rate of discounting predicts treatment response (Washio et al., 2011). Area Under the curve (AUC) values will be used to quantify the rate of discounting for each individual. 3. Wisconsin Card Sort, a measure of executive functioning and cognitive

flexibility, has been related to changes in commitment language during treatment (Aharonovich et al. 2008) and is currently being used in other funded studies (NIDA K23; An experimental model of human language and cognition in drug dependence PI: [name]). 4. The Behavior Rating Inventory of Executive Function (Adult Version (BRIEF-A; Rabin et al., 2006) is a 75-item standardized self-report measure that assesses an individual's perception of their self-regulation in their everyday environment. It yields nine reliable subscale scores reflecting executive functioning (e.g. inhibit, self-monitor) and two broader indices: Metacognition and Behavioral Regulation. The Behavioral Regulation score is the measure of interest, B. Implicit Cognition. We have shown that a stronger attentional bias towards cocaine related stimuli and stronger implicit beliefs about the positive consequences of cocaine use predict worse treatment outcome during behavioral interventions ([name] et al., 2006, 2012). The **Drug Stroop task** has been utilized by our group in other treatment studies ([name] et al., 2006) and will assess the strength of an attentional bias towards cocaine stimuli. The Implicit Relational Assessment Procedure (Barnes-Holmes, 2008) will assess the strength of implicit beliefs about the positive and negative consequences of cocaine use. **BEHAVIORAL** MECHANISM: Relapse Prevention Skills: Coping Strategies Scale (CSS) - Brief Version. (4 mins) (Litt et al., 2005) The utilization of coping skills is central to behavioral interventions for substance use. We will assess the extent to which patients report using the coping skills taught in the TES intervention. The CSS is a 23-item questionnaire (originally adapted from the Processes of Change questionnaire, Prochaska et al., 1988) that assesses coping skills such as problem solving and dealing with urges to use substances of abuse. This scale will be of primary importance to assess the extent to which the treatments differentially impact the development of coping skills. VERBAL MECHANISM: Commitment Language: Language is the primary vehicle of counseling interactions and it promotes self-regulation (Hayes et al., 1986). The strength of in-session commitment language predicts treatment outcome among substance abusers over a one-year period (Amrhein et al., 2003). Patient language will be coded with [name] (a consultant for this proposal) system at baseline and at week 5 (the first week individuals would be randomized to either MAS-ER or PLACEBO) and relate these assessments to treatment outcome. The DARN-C coding is reliable (Amrhein et al., 2003), [name] lab will code the therapy sessions; coders will be blind to patients outcomes and treatment assignments. For this set of analyses Baseline and Week 5 assessments will be used to predict treatment response (multiple comparison corrections will be used to reduce the chance of Type I errors).]

C14. Exploratory Analyses. A series of analyses will also be conducted to investigate the effect of each treatment condition on the key cognitive domains assessed and coping skills over time. The analysis of secondary outcomes collected over time will be based on Mixed Effect Models (MEM) for longitudinal data (Diggle et al., 2002). MEM requires no parametric distributional assumptions, provides robust inference with respect to misspecification of the covariance, and allows for the analysis of continuous, categorical and count data which may be missing for some patients either because of a missed week or due to drop-out, thus complete information for all patients is not needed. PROC NL MIXED or GLIMMIX in SAS will be used to carry out these analyses. The analyses will be used to separately test the effect of treatment condition on the magnitude of change between week 5 and week 14 for each the cognitive functioning domains and coping skill acquisition factors. Treatment condition and treatment by time interaction terms will be entered as predictors. This approach is potentially more sensitive to treatment effects since it incorporates each measurement period and effects of time. A treatment effect would be reflected in a significant main effect of either treatment or treatment by time interaction. If appropriate, baseline level of cocaine use will also be included as a covariate to test if it moderates the effect of treatment on the cognitive and behavioral outcome measures.

**Future Directions**: The proposed clinical trial seeks to identify key cognitive-verbal predictors of response to a behavioral intervention and test the efficacy of enhancing a behavioral treatment with amphetamine to improve treatment outcome among cocaine dependent individuals who fail to respond to the behavior therapy alone, arguably the subpopulation of patients most in need of pharmacotherapy. Identifying cognitive-verbal predictors of treatment response may help guide the refinement of behavioral treatment strategies. Further, similar to other areas of medicine, it may be that a dynamic, sequential treatment that integrates alternative intervention strategies based on patient response, will have greater efficacy than any one approach alone. If positive, the results of this trial may provide a rationale for further behavioral treatment development (Stage 1 or 2) or the investigation of this sequential treatment approach in community settings (i.e. a Stage III trial), which may set the stage for disseminating a critically important treatment strategy to the greater community of clinicians treating cocaine-dependent patients. In addition, this treatment paradigm can help stimulate further experimental research by providing a treatment platform that may help facilitate a better understanding of the neurobiological and cognitive underpinnings by which these interventions exert their effects.

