Behavioral therapies that impart skills and provide tangible incentives (contingency management, CM) for abstinence, e.g. the Community Reinforcement Approach (CRA), have shown the most robust and consistent effects in reducing cocaine use among dependent patients (Dutra et al., 2008; Higgins et al., 1994). Still, a significant proportion of individuals fail to respond to CM based interventions alone. Recent trials have suggested that combining CM interventions with medications that boost mono-amine functioning can enhance treatment response above that of either treatment alone (Kosten et al., 2003; Moeller et al., 2007; Poling et al., 2006; Schmitz et al. 2008). Our group, using an innovative imaging and treatment design, has further demonstrated that deficient dopamine transmission, measured with the PET 11C-raclopride displacement paradigm, predicts poor response to the Community Reinforcement Approach with CM (Martinez, [name], et al., 2011). This finding provides a key neurobiological target, suggesting enhancing behavioral interventions with a pharmacotherapy tailored to enhance dopamine transmission may provide a useful strategy to help boost treatment response among those individuals least likely to benefit from behavioral treatments alone.

Among available medications, stimulants produce the most direct and potent augmentation of dopamine release. Several studies (Anderson, et al., 2009; [name], 1998, Mooney et al., 2009), including a placebo-controlled trial that included mixed amphetamine salts-extended release (MAS-ER) recently completed at our center (see Significance Section), suggest an agonist replacement strategy with stimulants is effective for promoting abstinence in cocaine dependence. The beneficial effect of our medication intervention was most notable among the more severely dependent patients – a group that had a low placebo response rate and maybe less likely to respond to a behavioral therapy alone. Taken together, the above findings suggest that stimulant medication may be a particularly effective strategy for enhancing the efficacy of behavioral interventions among cocaine dependent patients who have failed to respond to behavioral therapy alone, a group we have demonstrated to evidence dopamine transmission deficits.

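### Is C8's 90% power overstated because its 37% against 10% comes from the pilot's high users on MAS-ER plus topiramate?

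*SAP*

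**What the plan says.** SAP section C8 gives two results from the pilot, both for MAS-ER combined with topiramate. For the whole sample: "We found 33.3% of the MAS-ER/topiramate group and 16.7% of the placebo group achieved 3 weeks of continuous abstinence in our controlled pilot study". For a subgroup: "The response was 37% in the MAS-ER/topiramate group compared to 7.4% in the placebo group among the high users".

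It then explains why this trial should see few placebo responders: "We expect our placebo response to be low since individuals randomized to a medication arm will have already demonstrated little response". On that footing it says "we conservatively estimated the power", "with an expected response rate of 37% in the ehancement medication arm (MAS-ER) compared to 10% among those receiving PLACEBO". The results are 80% power with 34 per arm and, for the larger number, "With 50 subjects in each arm there is 90% power to detect the same difference". C7 puts all 100 randomised patients in the primary analysis, so 50 per arm is the relevant size; 34 per arm matches the 68 completers in the Protocol's description of the subject population.

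Earlier in C8, after the power statement for the week-4 responder analysis (odds ratio 2.8), prior studies of amphetamine and of the computer-delivered therapy are said to "suggest medium effect sizes can be reasonably expected".

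**The concern.** The planned effect is larger than the pilot's overall result. As odds ratios, 37% against 10% is 5.3, the whole pilot is 2.5 and the high-user subgroup is 7.3. The word conservative therefore holds against the subgroup but not against the whole sample. C8's argument from non-response concerns the placebo rate; it gives no specific reason for taking 37% rather than 33.3% in the active arm, or for applying a rate observed with topiramate to a trial without it. The Protocol's background links high use to behavioural non-response only tentatively, calling high-severity patients "a group that had a low placebo response rate and maybe less likely to respond to a behavioral therapy alone".

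The stake would be a trial described as having 90% power that has closer to an even chance of detecting the effect seen in the pilot as a whole. A reader of a null result might then take it as stronger evidence against MAS-ER than it is.

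**Working it through.** **Inputs.** Rates from C8: 37%, 10%, 33.3%, 16.7%, 7.4%. Significance level 0.05 from C8. Patients per arm: 34 and 50, from C8 and C7. C8 does not state sidedness; two-sided is assumed, because one-sided 5% would give 85–87% at 34 per arm and 95–96% at 50 and so overshoot both stated figures.

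**Formulas**, with n per arm, p̄ the mean of the two rates and S = √[(p1(1−p1) + p2(1−p2))/n]:

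- pooled: power = Φ{[|p1−p2| − 1.96·√(2p̄(1−p̄)/n)] / S}
- unpooled: power = Φ{|p1−p2|/S − 1.96}

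**Step 1: reproduce C8 (37% against 10%).**

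- n = 50: p̄ = 0.235; √(2·0.235·0.765/50) = 0.0848; S = √[(0.2331 + 0.0900)/50] = 0.0804. Pooled: (0.27 − 0.1662)/0.0804 = 1.29, so 90.2%. Unpooled: 3.36 − 1.96 = 1.40, so 91.9%. Exact enumeration of the chi-square test gives 91.4%.
- n = 34: pooled 75.9%, unpooled 79.1%, exact chi-square 78.7%.

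The 90% is confirmed. The 80% holds to rounding by the unpooled and exact methods.

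**Step 2: whole-sample rates (33.3% against 16.7%), n = 50.** p̄ = 0.25; √(2·0.25·0.75/50) = 0.0866; S = √[(0.2221 + 0.1391)/50] = 0.0850. Pooled: (0.166 − 0.1697)/0.0850 = −0.04, so 48.2%. Unpooled: 1.953 − 1.960 = −0.007, so 49.7%. At these rates about 106 per arm would be needed for 80% power.

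**Step 3: change one rate at a time, n = 50.**

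| Active | Placebo | Where the rates come from | Pooled | Unpooled |
|---|---|---|---|---|
| 37% | 10% | C8's planning rates | 90.2% | 91.9% |
| 33.3% | 10% | whole-sample active, C8's placebo | 81.7% | 83.9% |
| 37% | 16.7% | C8's active, whole-sample placebo | 63.3% | 65.3% |
| 33.3% | 16.7% | whole sample in both arms | 48.2% | 49.7% |

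On the pooled figures, lowering the active rate to 33.3% costs 90.2 − 81.7 = 8.5 points. Then raising placebo from 10% to 16.7% costs a further 81.7 − 48.2 = 33.5 points. So most of the drop depends on the placebo rate.

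**Step 4: which placebo rate fits this design?** Under the Protocol's design overview, all participants first receive four weeks of the behavioural treatment and only those who do not respond are randomised; 155 enter and 100 are planned to be randomised. Neither document says that the pilot's patients were selected for such a failure. Removing early responders can lower the placebo rate among heavy and lighter users alike, so a rate below 16.7% does not require the randomised patients to resemble the pilot's high users. C8's 10% lies between the two pilot placebo rates, 7.4% and 16.7%.

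**The case for a change.** The strongest reply is that selection may work on both arms. Patients who fail the behavioural treatment may also respond less to medication. If the pilot's whole-sample odds ratio of 2.5 held at a 10% placebo rate, the active odds would be 2.5 × 0.1111 = 0.278 and the active rate 0.278/1.278 = 21.7%; 50 per arm would then have only about 36–37% power. The topiramate component is also missing from this trial, and C8 does not say whether its sentence about medium effects covers the primary comparison.

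Part of this stands. C8 offers one scenario and does not defend 37% for MAS-ER alone in non-responders. The rest goes less far:

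- The documents report no response rate for MAS-ER alone in patients who failed this behavioural treatment, so every alternative figure, including 36–37% and 48–50%, rests on an assumption of its own.
- The Protocol's background gives some support for a good active response: the pilot benefit was clearest in the more severely dependent, and poor responders to the behavioural treatment showed deficient dopamine transmission. This is tentative, but it does not depend on high use.
- The subgroup source is not concealed. C8 prints both pilot results, labels the subgroup and then uses its active rate; conservative reads most naturally as raising 7.4% to 10%.
- The missing definition of high use is not clearly a gap. The available SAP begins at C7, and the Protocol refers to a separate Significance section for the pilot.
- The remark about medium effects enters no calculation.

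On over-reading a null result, the confidence interval for the treatment effect shows which effects the data exclude. Planned power does not.

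**Conclusion.** No change to the plan follows. C8's power figures are right to rounding for the effect it states: 90–92% at 50 per arm and, by the unpooled and exact methods, about 79% at 34, two-sided 5%. The fall to 48–50% needs the pilot's placebo rate of 16.7% in a population selected for not having responded, which C8 gives a sound reason not to expect. With C8's placebo rate and the whole-sample active rate, power is 82–84%, still above 80%. The choice of 37% remains an optimistic assumption that C8 does not specifically defend, and true power could be well below 90% if the active rate is lower in these patients. That is ordinary planning uncertainty, with its source in plain view. A sensitivity line or a count of heavy users at baseline would inform a reader but would alter neither the 100 patients to be randomised nor the logistic regression in C10, and no result or conclusion would change. The conclusion assumes a two-sided test and 50 analysed per arm.

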This proposal will be one of the first investigations to employ a sequential and integrative treatment strategy in which a medication targeting dopamine release will be used to enhance the efficacy of a behavioral intervention among individuals not responding to the behavioral treatment alone. We propose a Stage 2 treatment development trial in which 155 treatment-seeking cocaine dependent participants will enter behavioral therapy based on the Community Reinforcement Approach (CRA + CM). Those who fail to achieve sustained abstinence after the first 4 weeks will continue with the behavioral treatment (CRA + CM) and be randomly assigned to receive either mixed amphetamine salts-extended release (MAS-ER) or placebo, over a 10-week double-blind trial.

The Primary Aim is to test the following hypothesis

Among cocaine dependent patients who have failed to respond to an initial trial of behavioral therapy (CRA + CM), a greater proportion in the enhanced behavioral treatment condition (CRA+CM/MAS-ER) will achieve 3-weeks or more of continued abstinence compared to patients treated with CRA+CM/PLACEBO.

We will also investigate cognitive and behavioral predictors of response to the behavioral therapy alone and the effect of medication enhancement on other indicators of treatment response: urine confirmed weekly cocaine use, craving, quality of life, and treatment retention. Potential moderators and mediators of an enhanced behavioral treatment effect, including cognitive functioning, the use of relapse prevention skills, and changes in patient commitment language will be tested.

Description of Subject Population

Sample #1

Specify subject population

Cocaine Dependent Treatment Seekers

Number of completers required to accomplish study aims

68

Projected number of subjects who will be enrolled to obtain required number of completers 155

Age range of subject population

18-60

Gender and Ethnic Breakdown

Males (total n=116): Hispanic n=35; Non-Hispanic n =81

Females (total n=39): Hispanic n=12; Non-Hispanic n= 27

American Indian: n=0

Asian: n=6 (Males=5; Females=1)

Native Hawaiian: n=0

African American: n=79 (Males=59; Females=20)

White: n=70 (Males=52; Females=18)

Description of subject population

We plan to enroll 155 adult participants who are actively using cocaine (evidenced by positive urine toxicology), are currently seeking treatment for their drug use and who meet eligibility criteria

Recruitment Procedures

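### With about 5 expected placebo successes, C10's covariate-by-treatment interaction tests are often inestimable or unreliable and the MAS-ER odds ratio is overstated if all four named covariates are used; the test of B1 is only mildly affected

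*SAP*

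**What the plan says.** C7 puts the primary analysis "on all 100 randomized patients". C8 plans "with an expected response rate of 37% in the ehancement medication arm (MAS-ER) compared to 10% among those receiving PLACEBO" and states that "With 50 subjects in each arm there is 90% power to detect the same difference".

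Under its primary hypothesis, C10 says the treatment effect on the binary outcome "will be examined using logistic regression adjusted for covariates (e.g., baseline days/week of cocaine use"). The model description that follows gives baseline cocaine use, age, gender and ethnicity as examples of the covariate vector. C10 then says "Covariate by treatment interactions will be tested for significance and the main effect", with the primary hypothesis answered by testing B1 = 0. It does not say whether the interactions are tested jointly or one at a time, or by likelihood-ratio, Wald or score test.

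The covariate set is not closed. C10's lists are illustrative, and C7 says that baseline variables that significantly predict the primary outcome will be considered as covariates.

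Neither document mentions sparse data, separation, or penalised or exact estimation, and neither gives a fallback if a model does not converge. C9's mixed models address dropout, which is a different matter.

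**The concern.** An intercept, treatment, four covariates and four interactions make 10 coefficients, to be fitted to about 23.5 successes. What limits the interactions is the placebo arm, with 5 expected successes. The Protocol's planned mix ("Females (total n=39): Hispanic n=12; Non-Hispanic n= 27", out of 155) puts about a quarter of those 5 among women and about 30% among Hispanic patients.

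If a subgroup of the placebo arm has no success, the maximum-likelihood estimate of its interaction with treatment is infinite. The Wald test is then meaningless, and the likelihood-ratio statistic no longer follows its chi-square distribution. Separately, maximum likelihood in small samples pushes log odds ratios away from zero, so the reported MAS-ER effect would tend to be too large.

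At stake are false or missing interaction results, which would cloud the reading of the main effect, and the effect size carried into the later-stage work foreseen in the SAP's Future Directions.

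**Working it through.** **Inputs.** 100 randomised (C7), taken as 50 per arm (C8). Response 37% vs 10%, alpha 0.05 (C8; two-sided assumed, since sidedness is not stated). Women 39/155; Hispanic 12 + 35 = 47/155 (Protocol, Gender and Ethnic Breakdown). The randomised patients are assumed to have the same mix as those enrolled.

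**The plan's own figure.** With unpooled variance, the number per arm for 80% power is

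(1.960 + 0.842)² × (0.37×0.63 + 0.10×0.90) / 0.27² = 34.8.

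The same formula gives 79.1% power at 34 per arm and 91.9% at 50. C8's 80% and 90% are reproduced to within 2 points. The pooled formula gives 38 per arm for 80% and 50 per arm for 90%; this difference does not affect the point.

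**Expected successes.** 50×0.37 + 50×0.10 = 18.5 + 5 = 23.5. The true odds ratio is (0.37/0.63)/(0.10/0.90) = 5.29.

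**Placebo subgroups.**
- Women: 50×39/155 = 12.6 patients, 1.3 expected successes.
- Hispanic: 50×47/155 = 15.2 patients, 1.5 expected successes.

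**Separation by direct arithmetic (placebo arm only, 10% response in every subgroup).** The chance that no placebo success falls in a group forming a share s of the arm is (1 − 0.10·s)^50.
- No success among women 28.0%, among men 2.0%, no success at all 0.5%. Successes fail to cover both sexes: 28.0 + 2.0 − 0.5 = 29.5%.
- No success among Hispanic patients 21.5%, among non-Hispanic patients 2.7%. Successes fail to cover both groups: 21.5 + 2.7 − 0.5 = 23.6% (unrounded inputs).
- Both failures together, from the planned sex-by-ethnicity cells (12, 27, 35, 81): 11.0%.
- At least one failure: 29.5 + 23.6 − 11.0 = 42.1%.

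Including the MAS-ER arm gives 42.7%.

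**Simulation of the full model.** Maximum likelihood, 50 per arm, the four covariates, all four interactions, no true interaction; main runs of 2,500 to 8,000 trials.

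| Quantity | Result |
|---|---|
| At least one interaction inestimable | 43-44% |
| Joint 4-df likelihood-ratio test, true null | about 10% (9.6-11.3%) |
| Joint score test, true null | about 7% |
| Joint Wald test, true null | about 0.6% |
| Median odds ratio, main-effects model | about 11-16% above truth (for example 5.9 or 6.1 against 5.3) |
| Median odds ratio, no covariates | 2-4% above truth |
| Test of B1, size | about 6-7% (LR), 3-5% (Wald) |
| Test of B1, power | 90-93% |
| Separation in the main-effects model | about 1% |

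**Dependence on the assumptions.**

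| Setting | Inestimable | Joint LR size | Median odds ratio |
|---|---|---|---|
| Baseline use only | 0.3-0.7% | 5.6-5.8% | +6% |
| Baseline use and age | 1.1-1.3% | 7.0-7.9% | +8% |
| All four, placebo rate 16.7% (C8's overall pilot) | 20% | 9% | +10% |
| All four, placebo rate 7.4% (C8's high users) | 59% | not reported | not reported |
| All four, 34 per arm | 63-66% | 13% | +17% to +21% |
| Three-level race in place of Hispanic yes/no | 95% | not reported | not reported |

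**Firth penalised likelihood, same model.** Estimates are always finite. The median odds ratio is about 1-5% below truth. The B1 test has size 4.9% (10% in both arms). Its power is 90.3% in one simulation (Wald 90.5%, LR 91.9%) and 91.8% in another (Wald 91.5%, LR 92.8%). The interaction tests reject a true null in 3-4% (gender alone) and 2.9% (joint).

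**The case against.** **The figures depend on the terms.** The only covariate in C10's first example is baseline use, and with that alone the problem nearly vanishes. The 43% comes almost wholly from the two binary interactions. This stands. A reader might infer that the flaw lies in the estimator whatever terms are chosen; the calculations do not support that. But C10 does name gender and ethnicity and does plan interactions, and C7 allows more covariates to enter, so the four-covariate model is a fair reading of the plan.

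**The primary test is sound.** A reader might infer that, because this is the primary analysis, type I error for the main hypothesis is in doubt. It is not, to any serious degree: the size and power of the B1 test stay close to nominal, and the treatment term rarely separates.

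**The 10% assumes a joint likelihood-ratio test.** C10 names no test, and the Wald test errs in the opposite direction. This stands as a condition on the figure. It also shows that the result turns on a choice the plan leaves open. If the four interactions are tested singly, at least one is significant in 24-26% of trials, but 1 − 0.95⁴ = 18.5% is ordinary multiplicity that a change of estimator would not remove.

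**The odds-ratio bias is small against its uncertainty.** The mean log-odds-ratio bias is about 0.18 against a sampling SD of about 0.64, and a typical 95% interval around an odds ratio of 6.0 runs from about 1.9 to 19. True: the bias would rarely change a conclusion. It is still systematic and cheap to remove.

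**C10 never says maximum likelihood.** Correct; that is the default meaning of logistic regression without further qualification. The gap is as much a missing provision for sparse data as a wrong method.

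**Conclusion.** The concern holds for the interaction tests and for the size of the reported odds ratio. At C8's rates with 50 per arm, ordinary maximum likelihood with the four named covariates and all four interactions leaves at least one interaction inestimable in about 43% of trials. The joint tests have true-null rejection rates from about 0.6% to about 10%, depending on an unnamed choice. The median odds ratio from the main-effects model is about 11-16% too high, of which 2-4 points arise without any covariates.

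This rests on taking C10's examples as the actual covariate set, Hispanic yes/no coding, the planned sex and ethnicity mix among randomised patients, and a 10% placebo rate. It would be worse with finer ethnicity coding, a lower placebo rate or fewer patients, and largely absent with baseline use alone. The documents do not support a claim that the confirmatory test of B1 fails. The change is worth making because it is cheap.

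**What to change.** In C10:

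- Fit the same model by Firth penalised logistic regression (the FIRTH option in PROC LOGISTIC).
- Test B1 by the penalised likelihood-ratio test and report a profile penalised-likelihood interval.
- Test each covariate-by-treatment interaction by the same penalised method in a separate model labelled supportive, not by ordinary Wald or likelihood-ratio tests.

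The cost is a few sentences of SAP text and one software option, with no change to sample size, endpoint or conduct. The median odds ratio would lie about 1-5% below the truth, and power for B1 would be at most about 1.6 points lower (91.9% to 90.3%). The interaction tests would be somewhat conservative. With about 1.3 expected successes among placebo women they would also remain weakly informative: Firth makes the estimate finite but does not supply the missing data.
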